6.2 Study Rationale

The current study is designed to confirm and extend the results observed in the Phase 1 and 2a studies with BMS-986036. Specifically, this study aims to demonstrate in participants with NASH and compensated cirrhosis, the efficacy of BMS-986036 using histological and noninvasive endpoints, and the safety of BMS-986036 as assessed by AEs, lab results and bone mineral density (BMD) monitoring.

The protocol was planned to randomize approximately 100 participants to 1 of 4 treatment groups (approximately 25 participants per group). This protocol amendment (Version 4.0) reflects that upon close of enrollment, approximately 155 participants were randomized to treatment (approximately 38 participants per group). The increased number of randomized participants occurred following: 1) unexpectedly high enrollment rate in the final month of the enrollment period; 2) several participants who had initially been enrolled into FALCON 1 (MB130-068) were determined (based on central pathology biopsy results) to qualify for FALCON 2 (MB130-069) during the period between the closure of enrollment and completion of randomization; and 3) an unexpected decrease in the actual screen failure rate for subjects entered in the final month of enrollment.

Based on the unmet medical need for patients, the benefit/risk assessment discussed in Section 6.3, and the strict safety monitoring of all participants, the potential clinical benefit outweighs the risks for those who have chosen to participate in this study. No additional revisions are required in Section 9 due to the increased number of randomized participants.

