- Child-Pugh Turcotte Score (see Section 8.5.1.7) at Screening, Day 1, Week 24, and Week 48/ET
- MELD Score (see Section 8.5.1.8) at each visit through Week 52/PTFU
- Liver-Related Clinical Outcome Events (see Section 8.5.1.9) at each visit from Day 1 through Week 52/PTFU
- Exploratory Biomarkers (see Section 8.5.2)
 - Transaminases at each visit through Week 52/PTFU
 - Adiponectin at Day 1, Week 4, Week 8, Week 12, Week 24, Week 48/ET, and Week 52/PTFU
 - PRO-C3 at Day 1, Week 4, Week 8, Week 12, Week 24, Week 48/ET, and Week 52/PTFU

- Health-related quality-of-life (HRQoL) questionnaires (see Section 8.5.1.10) at Day 1, Week 24, and Week 48/ET
 - 3-Level EuroQol 5 Dimension (EQ-5D-3L) questionnaire
 - 36-question Short Form (SF-36) quality-of-life questionnaire
 - Chronic Liver Disease Questionnaire-Nonalcoholic Fatty Liver Disease (CLDQ-NAFLD) questionnaire

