9. STATISTICAL CONSIDERATIONS

9.1 Sample Size Determination

The primary efficacy endpoint is the proportion of participants with a \geq 1-stage improvement in fibrosis (as defined by NASH CRN Fibrosis Score) without worsening of NASH (as defined by the NAFLD Activity Score) at Week 48, as determined by liver biopsy.

It is planned to randomize approximately 100 participants to 1 of the 4 treatment groups (approximately 25 participants per group), BMS-986036 10 mg QW, BMS-986036 20 mg QW, BMS-986036 40 mg QW or matching placebo QW in a 1:1:1:1 ratio.

A Cochran-Armitage trend test of proportions, with an estimated response rate of 15% for the primary endpoint for placebo and response rates for BMS-986036 10 mg QW, BMS-986036 20 mg QW, and BMS-986036 40 mg QW of 20%, 30%, and 40%, respectively, would provide at least 70% power at a 1-sided $\alpha = 0.05$ (based on original sample size estimate of approximately 100 participants). The final sample size was approximately 155 participants (see Section 6.2).

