For continuous endpoints the analysis of covariance (ANCOVA) models will be used to explore changes from baseline that include fixed factors for the treatment group and the corresponding covariate for baseline value for the following:

- Quantitative measurements of fibrosis and fat on biopsy
  - Assessment of qFibrosis using digital pathology
  - Assessment of CPA
  - Assessment of fat and alpha-SMA by morphometry
- Hepatic fat fraction as measured using MRI-PDFF
- Noninvasive measures of fibrosis and/or cirrhosis
  - Liver stiffness as determined by MRE
  - Fibroscan elastography results
  - APRI, FIB-4, and NAFLD scores
- Exploratory biomarkers
  - Transaminases ALT and AST
  - PRO-C3

A repeated measures analysis will model changes from baseline for each of the exploratory endpoints separately for data collected at planned visits using restricted maximum likelihood estimations. The model will include treatment group, visit, baseline value, treatment \* visit and baseline stratification factors as fixed effects. An unstructured covariance matrix will be used to represent the correlation of the repeated measures within each subject. This model will be used to provide point estimates for the treatment differences, standard errors for the differences, and corresponding 2-sided 95% confidence intervals for mean change from baseline at each time point. Statistical inferences for comparing treatment groups will utilize Kenward-Rodgers Degrees of Freedom.

Other biomarkers will be descriptively summarized by time point and will include percent change from baseline in addition to change from baseline.

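### SAP 6.4 lists no baseline-by-visit term in the repeated-measures model; if the baseline slope changes between visits, late-visit differences in exploratory markers are estimated less precisely than they could be

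*SAP*

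**What the plan says.** SAP 6.4 plans a likelihood-based repeated-measures model of change from baseline, fitted to each exploratory endpoint separately. On its fixed effects it says "The model will include treatment group, visit, baseline value", followed by the treatment-by-visit interaction and the stratification factors. On the covariance it says: "An unstructured covariance matrix will be used to represent the correlation of the repeated measures within each subject". The output is treatment differences with standard errors and "corresponding 2-sided 95% confidence intervals for mean change from baseline at each time point".

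The same section plans ANCOVA models "that include fixed factors for the treatment group and the corresponding covariate for baseline value for the following", and that list includes ALT, AST and PRO-C3. SAP 6.4 does not say at which visit the ANCOVA is fitted, or which analysis takes precedence when both address the same contrast.

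Protocol 8.5.1 sets the schedules: "Transaminases at each visit through Week 52/PTFU" and "PRO-C3 at Day 1, Week 4, Week 8, Week 12, Week 24, Week 48/ET, and Week 52/PTFU". Protocol 6.2 gives the trial size: "approximately 155 participants were randomized to treatment (approximately 38 participants per group".

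**The concern.** Treatment may act differently at each visit, and each visit has its own residual variance, but baseline enters with a single coefficient. If the regression of the later value on baseline flattens with time, the pooled coefficient lies between the early and late slopes, closer to the early ones because their residual variance is smaller. It then over-adjusts at the late visits, and the misfit adds to the residual variance there.

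A constant slope is not something these documents let one presume. The model pools on-treatment visits with Week 52, four weeks after treatment ends. Table 4 of the protocol projects drug effects as percentage changes. If effects are proportional, change scales with baseline, and the pooled slope would move as the effect builds and wanes. That is an inference, and it gives no size.

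At stake is the width of the late-visit intervals for markers that feed a dose-selection judgement. Protocol 6.2.1 says that later dose selection will rest on the totality of the analyses.

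**Working it through.** **Plan's own figure.** Neither document states a power or precision figure for ALT, AST or PRO-C3. The only power statement (Protocol 9.1) concerns the primary trend test, so there is nothing to reproduce on this point.

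**Inputs from the documents.**
- ALT/AST: Weeks 4, 8, 12, 16, 20, 24, 32, 40, 48, 52 (10 visits).
- PRO-C3: Weeks 4, 8, 12, 24, 48, 52 (6 visits).
- About 38 participants per arm.

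**Assumed inputs (not in the documents).** Equal unit variances at all visits. Correlation between visits s and t is c·exp(−g|s−t|), with g = ln(r4/r48)/44 and c = r4·exp(4g), where r4 and r48 are the baseline correlations at Weeks 4 and 48. Data are complete.

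**Formula.** Let β_t be the slope on baseline at visit t and S the residual covariance given baseline. The common slope converges to

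b = (1′S⁻¹β)/(1′S⁻¹1).

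The Week 48 standard error with a common slope, relative to visit-specific slopes, is

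ratio = √[1 + var(baseline)·(β₄₈ − b)² / S₄₈,₄₈].

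Modelling change from baseline shifts every slope by −1 and leaves the ratio unchanged.

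**Worked case, PRO-C3, 0.8/0.5.** b = 0.721, β₄₈ = 0.50 and S₄₈,₄₈ = 1 − 0.50² = 0.75. Ratio = √(1 + 0.221²/0.75) = √1.065 = 1.032.

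**Range, PRO-C3 schedule (ALT/AST agrees to within 0.2 percentage points).**

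| r4 / r48 | common slope b | Week 48 SE ratio |
|---|---|---|
| 0.6 / 0.6 | 0.600 | 1.000 |
| 0.7 / 0.6 | 0.663 | 1.003 |
| 0.8 / 0.6 | 0.746 | 1.016 |
| 0.8 / 0.5 | 0.721 | 1.032 |
| 0.8 / 0.4 | 0.694 | 1.050 |
| 0.9 / 0.5 | 0.838 | 1.074 |
| 0.9 / 0.3 | 0.808 | 1.133 |

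**Other visits.** On the ALT/AST schedule at 0.8/0.5, the loss is 0.9% at Week 4, 0.5% at Week 24 and 3.2% at Week 48, and it averages 1.2% over the ten visits. At 0.9/0.5 the average is 3.0%.

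**Sensitivity to the assumed structure.** With linear decay of the slope and a compound-symmetric residual correlation of 0.3 to 0.7, the Week 48 loss is about 2–4% at 0.8/0.6, 3–10% at 0.8/0.5 and 16–33% at 0.9/0.3. If the correlation falls from 0.81 to 0.57 only because late visits are noisier, with the slope constant, the ratio is 1.000.

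**Simulation check.** PRO-C3 schedule, 38 per arm, 300 trials per setting, strata omitted and no Kenward-Roger correction. Ratios of mean model-based SEs were 1.003 (0.7/0.6), 1.033 (0.8/0.5) and 1.133 (0.9/0.3) with complete data, and 1.003, 1.034 and 1.134 with 15% random dropout. Estimates were essentially unbiased under both models.

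**Against the planned ANCOVA.** An ANCOVA fitted at Week 48 has its own Week 48 slope. Setting the stratification factors aside, with complete data it matches the visit-specific-slope model at that visit. The ratios above therefore also compare the repeated-measures model with that ANCOVA.

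**The case against.** The strongest reply is that this is modelling preference. A common baseline slope is a valid and more parsimonious specification, estimates are unbiased either way, and the endpoints are exploratory, with no power claim or stated decision rule. The ANCOVA in the same section already escapes the constraint. The intervals are promised at every time point, so quoting Week 48 alone picks one of the worst-affected visits.

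Most of this stands and limits the weight of the point. The ANCOVA argument is only partial. The visit is not stated, and where slopes differ and data are complete, the more elaborate model would give the wider Week 48 interval of the two, with no rule on which to read.

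A reader might also infer that the plan definitely widens the Week 48 intervals because baseline predicts early visits much better than late ones. The documents do not support that. They report no by-visit correlation, slope or SD for these markers. The operative quantity is also a changing slope, not a falling correlation: with a constant slope and noisier late visits, nothing is lost. A headline loss of 6–12% would likewise describe only steep decay.

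**Conclusion.** The point holds in conditional form. The listed model imposes one baseline slope on all visits. If the true slopes differ, late-visit precision is lower than it need be. Under equal variances and exponential decay, the Week 48 standard error is 0–3% larger for flat to moderate decay (0.6/0.6 to 0.8/0.5), about 5–7% for steeper decay (0.8/0.4, 0.9/0.5) and 13% at 0.9/0.3. Strongly correlated residuals can raise these figures, and a constant slope removes the loss. For scale, a 7% larger SE is 1.07² = 1.145 times the variance, equivalent to losing 1 − 1/1.145 ≈ 13% of the sample.

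Which setting applies to ALT, AST or PRO-C3 cannot be read from the documents. The consequence is confined to the precision of exploratory endpoints. It does not introduce bias or touch the primary analysis, so this is a minor improvement, not a correction of an error.

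**What to change.** In SAP 6.4, add baseline value by visit to the fixed effects of the repeated-measures model, or state why a common slope is preferred. The cost is one parameter per visit beyond the first: 10 − 1 = 9 for ALT and AST and 6 − 1 = 5 for PRO-C3, with about 155 participants. If the slopes are in fact equal, almost nothing is lost. It would also help to state at which visit the ANCOVA is fitted and which analysis is read first when both estimate the same contrast.

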## 6.5 General Methodology

All analyses will use SAS® version 9.4 or higher.

- Descriptive summaries will be tabulated by treatment group and overall, unless otherwise specified.
- Categorical data will be presented using counts and percentages, with the number of participants in each category as the denominator for percentages
  - For by-visit summaries denominators may be adjusted to reflect the number of participants in the study at the time of the visit
  - Percentages will be rounded to one decimal place except 0% and 100% which will be displayed without any decimal places and percentages will not be displayed for zero counts.
- Continuous data will be summarized using the number of observations (n), mean, SD, median, first quartile, third quartile, minimum, and maximum. Minimum and maximum will be rounded to the precision of the original value.
  - Mean, median, first and third quartiles will be rounded to 1 decimal place greater than the precision of the original value. The SD will be rounded to 2 decimal places greater than the precision of the original value, with the original value having up to a maximum of 3 decimal places.

Sponsor: Bristol-Myers Squibb

Protocol No.: MB130-069

- P-values will be presented to 3 decimal places.

### **6.5.1 Participant Disposition**

The number and percentage of participants in each analysis population will be presented. The number and percentage of participants randomized but not treated will be included.

The number of participants randomized will be presented by treatment group, along with the number and percentage of participants who completed, discontinued, and are ongoing treatment or the study at the time of the data cut by treatment group.

Enrollment by country and center will be tabulated among randomized participants.

Also, by-participant listings will be generated.

### **6.5.2 Demographics and Baseline Disease Characteristics**

Demographics and baseline disease characteristics will be summarized by treatment group and overall for the mITT population. Individual participant listings will be provided to support the summary tables.

### **6.5.3 Medical History**

A summary of general medical history will be presented by Medical Dictionary for Regulatory Activities (MedDRA) Version 20.1 or higher SOC and PT for the safety population. The number and percentage of participants with each event will be presented by SOC and PT. Note that counting will be by participant not event and participants are only counted once within each SOC and PT.

A separate specific disease history table, including history of prior NASH therapy and history of Hepatitis C virus, will be provided by treatment group and total for the safety population. The proportion of participants with each type of disease history condition (e.g. history of type 1 diabetes, history of type 2 diabetes, etc.) will be included. These histories will be presented in participant listings.

Data collected on prior surgeries will be listed.

### **6.5.4 Prior Medications**

Prior medications summaries will be presented for the safety population by treatment group and overall. A summary showing the number and percentage of participants who had prior medications will be presented by World Health Organization (WHO) Anatomic Therapeutic Classification (ATC) level and preferred name, version WHO DD 2017 SEP01 DDE+HD or higher. Note that counting will be by participant and participants are only counted once within each ATC and PT.

### **6.5.5 Protocol Deviations**

Important protocol deviations will be summarized by number and percentage of participants experiencing each deviation category. All protocol deviations will be listed.

### **6.5.6 Treatments**

#### **6.5.6.1 Extent of Study Treatment Exposure**

Summary statistics for study exposure will be based on the safety population and presented by treatment group and pooled BMS-986036.

The following summaries will be included:

- Number of participants receiving at least 1 injection
- Number of participants with at least 1 injection not taken as planned and reason
- Frequency of the number of weeks of treatment (e.g. 16 weeks, 20 weeks, etc.)

Sponsor: Bristol-Myers Squibb

Protocol No.: MB130-069

- Continuous summary of treatment duration (in weeks)
- Summary of percentage of treatment completed

Participant listings will present exposure data at the injection-level. End of treatment reasons will be listed separately, as well as device malfunctions.

#### 6.5.6.2 Concomitant and Follow-up Medications

Concomitant medications (through Week 52 / PTFU), bone-density related medications and NASH therapies taken after the end of study treatment (Week 52/PTFU through 6-month Follow-up) will be presented separately among the safety population by treatment group and overall. The summaries will include the number and percentage of participants who had medications and will be presented by WHO ATC drug name and preferred name, version WHODD March 2015 or later. A participant listing of medications will be provided to support the tables.

#### 6.5.6.3 Diagnostic and Medical Procedures

Diagnostic and medical procedures will be presented in a participant listing.

#### 6.5.7 Delayed or Missed Study Visits Due to COVID-19

Any disruptions to study visits (resulting in missed or delayed visit) due to COVID-19 occurred during treatment period and post treatment follow-up will be summarized using mITT population. Patients with missed or delayed visits will be tabulated using frequency and percentage by study visit. A listing of patients reporting missed study visits due to COVID-19 will be presented.

### 7.0 Sequence of Planned Analyses

Locking, freezing, cleaning, and details for transferring of data will be described in a separate study plan.

#### 7.1 Week 52 Analysis

The Week 52 data analysis is based on all subjects who have completed the Week 52/PTFU visit. A data cut-off date of 08Oct2020 is applied to the raw data extract for the locked database. The study will continue to collect data for the long-term follow-up. in a blinded fashion.

- All Efficacy data will be summarized based on mITT principle for DB Lock defined by eCRF date cut-off 08Oct2020 on all participants who have completed liver biopsy.
- If the biopsies were delayed (due to impact of COVID-19 or other causes) and performed between Week 48 and Week 52, the biopsies results will be included in the planned Week 48 visit.
- Safety data will be summarized using Safety population through DB lock defined by eCRF date cut-off date of 08Oct2020.
- All available data beyond Week 52 will be summarized descriptively.

Sponsor and designee personnel may be unblinded once all participants have completed the Week 52/PTFU visit and all data have been collected through that time point to facilitate analyses. The list of TFLs to be provided for this analysis will be kept in a separate document outside the SAP.

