9.2 Populations for Analyses

The following populations are defined for analysis purposes:

Population	Description
Enrolled	All participants who sign informed consent.
Randomized	All participants who are randomized, analyzed as per randomized treatment.
Modified intent-to-treat (mITT)	All participants who are randomized and receive at least 1 dose of study medication, analyzed according to randomized treatment. All primary efficacy analyses will be conducted using this population.
As treated (Safety)	All participants who are randomized and receive at least 1 dose of study medication, analyzed according to treatment actually received. This population will be essentially the same as the mITT unless a participant received an incorrect treatment, i.e., a treatment different from what he/she was randomized to. All safety analyses will be conducted using this population.

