## 5.0 Analysis Populations

- Enrolled Population: All participants who sign informed consent.
- Randomized Population: All participants who are randomized, analyzed as per randomized treatment.
- Modified intent-to-treat (mITT) Population: All participants who are randomized and receive at least 1 dose of study medication, analyzed according to randomized treatment. All primary efficacy analyses will be conducted using this population.
- As Treated (Safety) Population: All participants who are randomized and receive at least 1 dose of study medication, analyzed according to treatment actually received. This population will be essentially the same as the mITT unless a participant received an incorrect treatment, i.e., a treatment different from what he/she was randomized to. All safety analyses will be conducted using this population.
- Pharmacokinetic (PK) Populations: All randomized participants who receive at least 1 dose of BMS-986036 and have any available concentration-time data. Available concentration-time data includes results that may be less than the lower limit of quantification (LLOQ). [REDACTED]

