#### 6.1.1 Primary Efficacy Analysis

The primary efficacy endpoint is the proportion of participants who achieve a  $\geq 1$ -stage improvement (as defined by NASH CRN Fibrosis Score) in fibrosis without worsening of NASH (as defined by NAFLD Activity Score) at Week 48, as determined by liver biopsy.

Improvement in fibrosis is defined as a decrease of fibrosis by  $\geq 1$  point, as determined by the NASH CRN Fibrosis Score. Worsening of NASH is defined as an increase of the NAFLD Activity Score (NAS) by  $\geq 1$  point.

Participants will be stratified at randomization by country (Non-Japan versus Japan). Participants in countries other than Japan will be stratified at randomization according to Type 2 Diabetes Mellitus (T2DM) status (yes versus no). Japanese participants will not be further stratified.

If lack of response in the strata prohibits analysis, the strata may be reduced to Japan/Non-Japan only or no stratification at all.

Sponsor: Bristol-Myers Squibb

Protocol No.: MB130-069

A Cochran-Armitage trend test of proportions at a one-sided 0.05 level of significance will be used to examine the linear trend among the proportions across treatment groups. The null hypothesis states that there is no association between treatment level and fibrosis stage improvement. The alternative hypothesis states that there is an association between treatment level and fibrosis stage improvement.

The proportion of participants with response will be summarized by strata as well as overall for each treatment group. Shift tables will be presented for the NAFLD Activity Score and NASH CRN Fibrosis Score. A bar chart of response/non-response in the primary endpoint will be provided.

All participants who prematurely discontinue from treatment without a biopsy at Week 48 (or ET, if applicable) or otherwise have a missing Week 48 (or ET, if applicable) biopsy result will be considered non-responders for the primary analysis of the primary efficacy endpoint.

All biopsy results will be included in the participant listings.

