#### 6.1.2 Secondary Efficacy Analyses

All secondary efficacy analyses will be conducted among the mITT population using the same methodology as the primary efficacy analysis. A completer analysis is not planned for secondary efficacy analyses.

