## 6.4 Exploratory Analyses

Analyses for exploratory endpoints (including biomarkers) will be performed using the mITT or safety populations. Categorical and continuous data will be summarized descriptively as presented in SAP [Section 6.5](#).

Exploratory dichotomous response variables will be summarized in a manner similar to that used for the primary and secondary efficacy analyses:

- Assessment of NASH CRN Fibrosis Score at Week 48
  - Proportion of participants with  $\geq 1$  stage improvement
  - Proportion of participants with  $\geq 2$  stage improvement
  - Proportion of participants with  $\geq 2$  stage improvement without worsening of NASH
  - Proportion of participants with NASH resolution
  - Proportion of participants with NASH improvement
- Assessment of Ishak Fibrosis Score at Week 48
  - Proportion of participants with  $\geq 1$  stage improvement
  - Proportion of participants with  $\geq 2$  stage improvement
- Assessment of CPA at Week 48
  - Proportion of participants with any improvement
- Hepatic fat fraction as measured using MRI-PDFF at Week 24 and Week 48
  - Proportion of subjects with  $\geq 30\%$  relative reduction,  $\geq 20\%$  relative reduction,  $\geq 10\%$  relative reduction, and  $\geq 5\%$  absolute reduction
- Liver stiffness as determined by MRE at Week 24 and Week 48
  - Proportion of subjects with  $\geq 19\%$  reduction
  - Proportion of subjects with  $\geq 15\%$  reduction
- Fibroscan elastography results at Week 48
  - Proportion of subjects with any improvement

In addition, summaries of  $\geq 1$  stage improvement, no change, and worsening will be tabulated and graphically presented for NASH CRN Fibrosis Score, Ishak Fibrosis Score, and NAS Total at Week 48. Participants without a Week 48 (or ET result) will be classified into the "Worse" category for these exploratory summaries.

Similarly to the primary and secondary efficacy endpoints, for exploratory endpoints based off the liver biopsy, the Week 48 result or ET biopsy will be used for Week 48 derivations. Participants without a Week 48 or ET biopsy will be classified as non-responders for liver biopsy endpoints at Week 48. Early termination visits for non-biopsy endpoints such as imaging and biomarkers may occur at other time points and will not

Sponsor: Bristol-Myers Squibb

Protocol No.: MB130-069

be summarized together with Week 48. For non-biopsy endpoints, ET will be summarized separately in the summary tables.

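### SAP 7.1 limits all Week 52 efficacy summaries to participants with a completed liver biopsy, against the plan's mITT and non-responder rules

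*SAP*

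**What the plan says.** The first bullet of SAP 7.1 (Week 52 Analysis) governs all efficacy data at this lock. It says they are "summarized based on mITT principle for DB Lock defined by eCRF date cut-off 08Oct2020 on all participants who have completed liver biopsy". The sentence that opens the section also bases the Week 52 analysis on subjects who completed the Week 52/PTFU visit.

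Elsewhere the plan keeps every randomized and dosed participant:

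- **Population.** Protocol 9.2 defines mITT as "All participants who are randomized and receive at least 1 dose of study medication, analyzed according to randomized treatment". SAP 5.0 has the same definition: after randomization, a participant must "receive at least 1 dose of study medication, analyzed according to randomized treatment. All primary efficacy analyses will be conducted using this population". Neither asks for a biopsy.
- **Primary endpoint.** Under SAP 6.1.1, participants with a missing Week 48 or ET "biopsy result will be considered non-responders for the primary analysis of the primary efficacy endpoint". Protocol 9.5.2.1 has the same rule. It adds a separate completer analysis, for the primary endpoint only.
- **Secondary endpoints.** SAP 6.1.2: "All secondary efficacy analyses will be conducted among the mITT population using the same methodology as the primary efficacy analysis", and "A completer analysis is not planned for secondary efficacy analyses".
- **Exploratory biopsy endpoints.** SAP 6.4: "Participants without a Week 48 or ET biopsy will be classified as non-responders for liver biopsy endpoints at Week 48".
- **Other exploratory endpoints** (MRI-PDFF, MRE, PRO-C3 and so on). SAP 6.4: "Analyses for exploratory endpoints (including biomarkers) will be performed using the mITT or safety populations".

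**The concern.** The bullet contradicts itself: it invokes the mITT principle and then names a narrower set of people. A programmer who follows its last words drops from the denominator the participants whom SAP 6.1.1, 6.1.2 and 6.4 keep as non-responders. The same words would make imaging and serum endpoints depend on having had a biopsy.

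The affected group is foreseeable. Protocol 8.5.1.1 calls for an ET biopsy only from Week 20, and those who leave earlier are merely asked to consider one. The SAP also expects visits missed or delayed because of COVID-19.

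The denominator of the primary response rates is at stake, and with it the trend p-value. If the point stays open, the choice between two denominators could be made after unblinding.

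**Working it through.** **1. Can the rest of the text settle it?** SAP 6.1 applies mITT to all efficacy analyses, but with an exception for cases specified otherwise. SAP 7.1 could be taken as such a case, and no section says which text prevails. As a data-cut rule the biopsy qualifier adds little: the same bullet already gives the cut-off date, delayed biopsies have their own bullet, and the safety bullet states its cut without any completion condition. SAP 6.1.2 implies that a completer analysis of the primary endpoint exists, but SAP 6.1.1 and 6.1.1.1 list none. That leaves SAP 7.1 as the only SAP text that names a biopsy-completed set, and it applies that set to all efficacy data.

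**2. Reproduce the plan's power (protocol 9.1).** Inputs: rates 15/20/30/40%, 25 per arm, Cochran-Armitage trend test, one-sided 0.05. With equally spaced scores s = 0 to 3 and w = s minus the mean score:

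- mean of the statistic: Σnwp = 25 × (−1.5×0.15 − 0.5×0.20 + 0.5×0.30 + 1.5×0.40) = 10.625
- null variance: p̄(1−p̄)Σnw² = 0.2625 × 0.7375 × 125 = 24.20, SD 4.919
- alternative variance: Σnw²p(1−p) = 22.98, SD 4.794
- power: Φ[(10.625 − 1.645×4.919)/4.794] = Φ(0.528) = 70.1%

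The protocol states at least 70%, so the figure reproduces. At 155 participants (39/39/39/38) the formula gives 85.6% and simulation about 86.1%.

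**3. Compare the two denominators.** The missing-biopsy rates are assumptions. There were 400,000 simulated trials per scenario (4,000,000 for size under the gradients). Each cell gives power in %, biopsy-completer / non-responder rule. The two columns bracket the mechanism: the missing are all non-responders, or missingness is independent of response.

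| Missing, placebo to 40 mg | Missing are non-responders | Missing at random |
|---|---|---|
| 5% in every arm | 86.7 / 86.0 | 84.5 / 83.9 |
| 10% in every arm | 87.4 / 86.1 | 82.7 / 81.5 |
| 15% in every arm | 88.1 / 86.1 | 80.8 / 78.9 |
| 20% in every arm | 88.9 / 86.0 | 78.7 / 76.2 |
| 5/6.7/8.3/10% | 90.0 / 86.1 | 83.6 / 78.7 |
| 10/8.3/6.7/5% | 83.5 / 86.2 | 83.7 / 86.2 |
| 5/10/15/20% | 95.3 / 86.2 | 81.4 / 65.5 |
| 20/15/10/5% | 74.6 / 86.1 | 81.8 / 90.3 |

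The gaps are 0.6 to about 2.8 points with equal missingness, 2.6 to 4.9 with a twofold gradient (about 12 of 155 missing) and 8.5 to 15.9 with a fourfold gradient (about 19 of 155).

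**4. Size.** Suppose the planned endpoint has a common 15% response and all the missing are non-responders. With 5/10/15/20% missing, the completer rates become 0.15/0.95, 0.15/0.90, 0.15/0.85 and 0.15/0.80, that is 15.8/16.7/17.6/18.8%: a trend created by the denominator alone. On expected counts of 37.05/35.1/33.15/30.4, Σnwp = 1.651 and the null SD is 4.883. The approximate rejection rate is the upper tail beyond 1.645 − 1.651/4.883 = 1.307, about 9.6%. Simulated rejection rates are:

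| Gradient | Completer, rising / reversed | Non-responder rule |
|---|---|---|
| Twofold | 6.3% / 4.1% | 5.0% |
| Fourfold | 9.8% / 2.4% | 5.0% |

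With equal missingness the completer test stays at 5.0 to 5.1%. Under missingness at random with unequal rates, the planned endpoint's response rates truly differ by arm, so those rejection rates are not size and are not given.

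**The case against.** The strongest reply is that SAP 7.1 concerns timing and data cuts, not populations. The contested words follow directly on the lock date, the bullet names the mITT principle, and SAP 6.1.1 is the more specific text for the primary endpoint. On that reading the qualifier only describes which biopsies are in the 08Oct2020 extract. It also names no visit, so an ET biopsy could count, and the set would be participants with any follow-up biopsy rather than strict Week 48 completers. For continuous biopsy measures (CPA, qFibrosis, fat, alpha-SMA) SAP 6.4 has no non-responder rule, so there the words merely describe who has data. Dropping imaging or serum data for want of a biopsy is the least likely application.

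Much of this stands. The data-cut reading is plausible, the larger figures depend on assumed gradients for which the documents give no evidence, and the point should not be read as proof that a completer analysis was intended. It does not remove the problem, because the data-cut meaning is nowhere written and the stated rule gives the wrong denominator if followed.

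**Conclusion.** The concern holds. As written, SAP 7.1 sets an efficacy denominator that conflicts with protocol 9.2 and 9.5.2.1 and with SAP 5.0, 6.1.1, 6.1.2 and 6.4. It should be fixed before lock.

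The practical size depends on two unknowns: which reading the sponsor intends, and how missing biopsies fall across arms. Under the data-cut reading the effect is nil. Under the literal reading it is minor if missingness is balanced. If missingness differs by arm it is material, and the direction follows the gradient: with missingness rising with dose, the completer set favours finding a trend; with it falling, the set works against one. All figures assume 155 participants, the planned response rates (or a common 15% for size), equally spaced scores and the stated missingness patterns.

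**What to change.** In SAP 7.1, delete the biopsy-completion qualifier from the first bullet and put in its place text to this effect:

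> Efficacy is summarized on the populations named in Sections 6.1 and 6.4 (full mITT for primary and secondary endpoints). Missing Week 48/ET biopsies are handled as in Sections 6.1.1, 6.1.2 and 6.4, as non-response for biopsy responder endpoints. The 08Oct2020 cut-off determines only which data are included. Completion of the Week 52/PTFU visit is the timing trigger for the analysis, not a condition for including a participant.

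The last sentence also repairs the opening line of the section, which has the same defect. The safety bullet can stay. Any biopsy-completer summary of the primary endpoint should be labelled as the supportive completer analysis of protocol 9.5.2.1.

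Two optional clarifications, neither an error: list that completer analysis in SAP 6.1.1.1, and say how a biopsy taken after Week 52 is mapped.

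The cost is a wording change in one section. SAP 1.0 already provides for tracked updates approved before lock, and no new table is needed because the completer analysis is already in the protocol.
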